7.2 Analysis Sets

For the randomized set, the frequency and percentage of the subjects included in FAS, PPS, and Safety Set are presented. The reason for the exclusion from each analysis set is presented with frequency and percentage. Also, a list of subjects included or excluded in the analysis set is complied.

A summary of the data is presented in the following table and list.

- T. Analysis Set (Randomized Set)
- L. Analysis Sets (Randomized Set)

7.3 Protocol Deviations

For the randomized set, the frequency, percentage and the number of occurrence of serious deviations from the protocol are presented and the list of subjects who experienced a major deviation of the protocol is compiled.

A summary of the data is presented in the following table and list.

- T. Major Protocol Deviation (Randomized Set)
- L. Major Protocol Deviation (Randomized Set)

Protocol No.: DW_UDCA005 English Translation Version

8. EFFICACY EVALUATION

8.1 Demographic and Baseline Characteristics

For the FAS, demographic information and baseline characteristics are summarized by each treatment group. For continuous data, mean, standard deviation, median, minimum, and maximum values are presented. For categorical data, frequency and percentage are presented. The differences among the treatment groups will be compared using the ANOVA or a Kruskal–Wallis test according to the normality test results for continuous data, and the chi-square test or Fisher's exact test for categorical data.

Demographics

- Continuous variables: Age (year), Height (cm), Weight (kg), BMI (kg/m²)
- Categorical variables: Sex (Male, Female), Smoking Status (Yes, No, Ex-smoker), Drinking Status (Yes, No, Ex-drinker)

Baseline Characteristics

- Continuous variables: Disease duration(month)
- Categorical variables: TNM stage (T: 1, 1a, 1b, 2, 3, 4, 4a, 4b, other / N: 0, 1, 2, 3, 3a, 3b, other / M: 0, 1, other), Stage (IA, IB, IIA, IIB, IIIA, IIIB, IIIC, IV), Gastrectomy type (Total gastrectomy, Distal gastrectomy, Proximal gastrectomy), Gastrotomy method (Open surgery, Laparoscopic surgery, Other), Lymph Nodes Resection Range (D1+, D), Stomach Reconstruction (Yes, No), Stomach Reconstruction type (Billoth I, Billoth II, Roux-en-Y, Other), Supportive anticancer treatments (Yes, No), Supportive anticancer treatments type (Chemotherapy, Radiotherapy, Other), ECOG performance status at screening (0,1)
 - Disease duration (month)
 - = (Randomization Date Diagnosis date of Gastric Cancer +1) x 12/365.25

In calculating the disease duration, if the month and/or day under the diagnosis day is noted UK, then it is replaced it with "01". If the year is noted "UK", then exclude it from the disease duration analysis.

A summary of the data is presented in the following tables.

- T. Demographics (FAS)
- T. Baseline Characteristics (FAS)

8.2 Medical History, Concurrent Disease and Surgery

The medical history is classified as past medical history or concurrent disease according to section 6.2. Past medical history, concurrent disease and prior surgery are standardized as "System Organ Class (SOC)" and "Preferred Term (PT)" using MedDRA version 20.0 or higher, and for the FAS, the frequency (N) and percentage (%) are summarized by each treatment group. The differences among treatment groups will be compared using the chi-square test or Fisher's exact test.

Protocol No.: DW_UDCA005 English Translation Version

A summary of the data is presented in the following tables.

- T. Past Medical History by SOC and PT (FAS)
- T. Current Disease by SOC and PT (FAS)
- T. Prior Surgery by SOC and PT (FAS)

8.3 Treatment Compliance and Medication Other Than Study Drug

8.3.1 Treatment Compliance

Treatment compliance by visit and overall treatment compliance are presented with the descriptive statistics (number of subjects, mean, standard deviation, median, minimum, and maximum values) and ANOVA or Kruskal-Wallis test is performed to examine the difference among treatment groups. A summary of the treatment compliance is presented for the FAS.

A summary of the data is presented in the following tables.

- T. Treatment Compliance (FAS)

8.3.2 Prior and Concomitant Medication

Medications are categorized according to Section 6.3 and standardized as Anatomical Main Group (ATC level 1) and Therapeutic Subgroup (ATC level 2) using WHO Drug Dictionary Enhanced 2017 or higher. For the FAS, prior and concomitant medications are summarized by frequency (N), percentage (%) and number of occurrence by each treatment group, and the differences among treatment groups are compared using the chi-square test or Fisher's exact test.

A summary of the data is presented in the following tables.

- T. Prior Medications by Anatomical Main Group and Therapeutic Subgroup (FAS)
- T. Concomitant Medications by Anatomical Main Group and Therapeutic Subgroup (FAS)

8.4 Efficacy Analysis

The efficacy assessment will be performed based on the FAS and the PPS groups. The FAS group result is considered as the main analysis, but the result of the PPS group should also be presented for the sensitivity analysis.

8.4.1 Primary Efficacy Analysis

The primary efficacy endpoint is the percentage of subjects with gallstone formation within 12 months of gastrectomy based on the external investigator's assessment.

For the superiority test of DWJ1319 over placebo on the incidence of gallstone formation, sequential multiple testing will be performed for each treatment group according to the fixed sequence method.

Step 1: Superiority testing for DWJ1319 600 mg compared with placebo (5% significance level)

Protocol No.: DW_UDCA005 English Translation Version

Step 2: Superiority testing for DWJ1319 300 mg compared with placebo (5% significance level)

As DWJ1319 600 mg is expected to be relatively more effective in preventing gallstones compared to DWJ1319 300 mg, the efficacy assessment of DWJ1319 600 mg versus placebo is given priority.

The step 2 test can be performed only if the result of the step 1 test is statistically significant, and conclusions about the superiority of DWJ1319 over placebo will be drawn based on the test result from each step. If the result of the step 1 test is not statistically significant, the step 2 test will not be performed, and it will be concluded that both treatment groups of DWJ1319 have failed to demonstrate superiority over placebo.

The frequency, percentage (%), and corresponding 95% confidence intervals are presented for the subjects with gallstone formation within 12 months by each treatment group. The comparison between each treatment group of DWJ1319 versus the placebo is analyzed using the Logistic Regression Model, with the lymph node resection range (D1+, D2) and the type of gastrectomy (Total gastrectomy, partial gastrectomy) as the covariates and the respective factors are defined as the following. The factors are defined as treatment group (DWJ1319 600 mg vs Placebo) for Step 1, treatment group (DWJ1319 300 mg vs Placebo) for Step 2, and treatment group (Placebo, DWJ1319 600 mg and DWJ1319 300 mg) for sensitivity analysis. Logistic Regression Model results are presented as odds ratios, corresponding 95% confidence intervals and two-sided p-values, and p-value is used for the final determination.

A summary of the data is presented in the following tables.

- T. Percentage of Subjects with Gallstone Formation within 12 month by the External Investigator's Assessment [DWJ1319 600mg vs Placebo] (FAS)
- T. Percentage of Subjects with Gallstone Formation within 12 month by the External Investigator's Assessment [DWJ1319 300mg vs Placebo] (FAS)
- T. Percentage of Subjects with Gallstone Formation within 12 month by the External Investigator's Assessment (FAS)
- T. Percentage of Subjects with Gallstone Formation within 12 month by the External Investigator's Assessment [DWJ1319 600mg vs Placebo] (PPS)
- T. Percentage of Subjects with Gallstone Formation within 12 month by the External Investigator's Assessment [DWJ1319 300mg vs Placebo] (PPS)
- T. Percentage of Subjects with Gallstone Formation within 12 month by the External Investigator's Assessment (PPS)

8.4.2 Secondary Efficacy Analysis

1) Percentage of subjects forming gallstones within 3, 6, 9, and 12 months from

Protocol No.: DW UDCA005

English Translation Version

gastrectomy

- 2) Percentage of subjects forming gallstones within 3, 6, and 9 months from gastrectomy as assessed by the external investigator
- 3) Percentage of subjects forming biliary sludge within 3, 6, 9, and 12 months from gastrectomy

For the secondary endpoints 1), 2), and 3), the comparison between each treatment group of DWJ1319 versus the placebo is analyzed using the Logistic Regression Model, with the treatment groups (DWJ1319 600 mg/DWJ1319 300 mg vs Placebo) as the factor and the lymph node resection range (D1+, D2) and the type of gastrectomy (Total gastrectomy, partial gastrectomy) as the covariates. Logistic Regression Model results are presented as odds ratios, corresponding 95% confidence intervals and two-sided p-values.

4) Time to gallstone formation

For the time to gallstone formation, the median and corresponding 95% confidence intervals, and standard error values are presented. The comparison between each treatment group of DWJ1319 versus the placebo is analyzed using the Cox Proportional Hazards regression Model and the two-sided p-values are presented, with the treatment groups (DWJ1319 600 mg/DWJ1319 300 mg vs Placebo) as the factor and the lymph node resection range (D1+, D2) and the type of gastrectomy (Total gastrectomy, partial gastrectomy) as the covariates.

A summary of the data is presented in the following tables.

- T. Percentage of Subjects with Gallstone Formation within 3, 6, 9, 12 month by the Investigator's Assessment (FAS)
- T. Percentage of Subjects with Gallstone Formation within 3, 6, 9, 12 month by the Investigator's Assessment (PPS)
- T. Percentage of Subjects with Gallstone Formation within 3, 6, 9 month by the External Investigator's Assessment (FAS)
- T. Percentage of Subjects with Gallstone Formation within 3, 6, 9month by the External Investigator's Assessment (PPS)
- T. Percentage of Subjects with Biliary Sludge Formation within 3, 6, 9, 12 month by the Investigator's Assessment (FAS)
- T. Percentage of Subjects with Biliary Sludge Formation within 3, 6, 9, 12 month by the Investigator's Assessment (PPS)
- T. Time to Gallstone Formation (FAS)
- T. Time to Gallstone Formation (PPS)

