8.3. Targeted Number of Subjects and Justification

1) Number of Subjects to be Recruited

Taking into account the 20% withdrawal rate, this clinical study plans to enroll a total of 519 subjects (173 per group).

2) Calculation Basis

The primary objective of this study is to assess the efficacy of the study drug compared with placebo in preventing gallstone formation after gastrectomy in patients with gastric cancer. If the efficacy of DWJ1319 300 mg or 600 mg versus placebo is statistically significant, the study drug is considered to demonstrate its superiority. The endpoints are the proportion of subjects with gallstone formation within 12 months after gastrectomy. The hypothesis to test this is as follows:

$$H_0$$
 (null hypothesis): $P_{T1} = P_C$ and $P_{T2} = P_C$
 H_1 (alternate hypothesis): $P_{T1} \neq P_C$ or $P_{T2} \neq P_C$

P_{T1}: Proportion of subjects with gallstone formation after receiving 600 mg of DWJ1319

P_{T2}: Proportion of subjects with gallstone formation after receiving 300 mg of DWJ1319

Pc: Proportion of subjects with gallstone formation after receiving placebo

For testing of each treatment group versus the placebo, the significance level of the test is not corrected because a sequential multiple test (twice) is performed using the fixed sequential method. The test sequence is 600 mg of DWJ1319 versus placebo and 300 mg of DWJ1319 versus placebo.

The following results were referenced to calculate the number of subjects to be tested.

	Placebo	Ursodiol	Ursodiol	Ursodiol
	1 100000	300 mg	600 mg	1,200 mg
Study 1 ¹⁹⁾ (6M)	32.14% (18/56)	13.21% (7/53)	1.64% (1/61)	6.35% (4/63)
Study 2 ⁴⁾ (12M)	16.94% (112/661)	-	-	-
Study 3 ⁷⁾ (12M)	13.64% (6/44)	-	-	-

In this clinical study, the incidence of gallstones in placebo was estimated to be 18%, which is the weighted average of Studies 1, 2 and 3, where Study 1 is the result of placebo in obese patients who underwent gastrectomy and Studies 2 and 3 are the adjusted results of placebo in gastric cancer patients who underwent gastrectomy. Since it is difficult to estimate the incidence of gallstone of DWJ1319 by each dose, 7%, which is the weighted average of the three Ursodiol treatment groups in Study 1 was estimated as the rate of gallstone formation for the study drug.

In addition to the above assumptions, the significance level is 5% for two-sided test, 80% for test power, and the minimum number of subjects for 1:1:1 assignment is as follows:

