4.6 Determination of the Sample Size

1) Number of Subjects to be Recruited

Taking into account the 20% withdrawal rate, this clinical study plans to enroll a total of 519 subjects (173 per group).

Protocol No.: DW_UDCA005 English Translation Version

2) Calculation Basis

The primary objective of this study is to assess the efficacy of the study drug compared with placebo in preventing gallstone formation after gastrectomy in patients with gastric cancer. If the efficacy of DWJ1319 300 mg or 600 mg versus placebo is statistically significant, the study drug is considered to demonstrate its superiority. The endpoint is the percentage of subjects forming gallstones within 12 months of gastrectomy. The hypothesis to test this is as follows:

 H_0 (Null hypothesis): $P_{T1} = P_C$ and $P_{T2} = P_C$ H_1 (Alternative hypothesis): $P_{T1} \neq P_C$ or $P_{T2} \neq P_C$

P_{T1}: Proportion of subjects forming gallstones after taking 600 mg of DWJ1319

P_{T2}: Proportion of subjects forming gallstones after taking 300 mg of DWJ1319

P_C: Proportion of subjects forming gallstones after taking placebo

For testing of each treatment group versus the placebo, the significance level of the test is not corrected because a sequential multiple test (twice) is performed using the fixed sequece method. The test sequence is 600 mg of DWJ1319 versus placebo and 300 mg of DWJ1319 versus placebo.

The following results were referenced to calculate the number of subjects to be tested.

	Placebo	Ursodiol	Ursodiol	Ursodiol	
Placebo		300 mg	600 mg	1,200 mg	
Study 1 (6M)	32.14% (18/56)	13.21% (7/53)	1.64% (1/61)	6.35% (4/63)	
Study 2 (12M)	16.94% (112/661)	-	-	-	
Study 3 (12M)	13.64% (6/44)	-	-	-	

In this clinical study, the incidence of gallstones with placebo was estimated to be 18%, which is the weighted average of study 1, 2 and 3, where study 1 is the result of placebo in obese patients who underwent gastrectomy and studies 2 and 3 are the adjusted results of placebo in patients with gastric cancer who underwent gastrectomy. Since it is difficult to estimate the incidence of gallstone of DWJ1319 by each dose, 7%, which is the weighted average of the three Ursodiol treatment groups in study 1, was estimated as the rate of gallstone formation for the study drug.

In addition to the above assumptions, the significance level is 5% for two-sided test, 80% for test power, and the minimum number of subjects for 1:1:1 assignment is as follows.

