$$\begin{split} N &= \frac{\left(Z_{1-2/\alpha} + Z_{1-\beta}\right)^2 \left\{P_T(1-P_T) + P_C(1-P_C)\right\}}{\delta^2} \\ &= \frac{(1.96 + 0.842)^2 \left\{0.07(1-0.07) + 0.18(1-0.18)\right\}}{(0.07 - 0.18)^2} \approx 138 \end{split}$$

Protocol No.: DW_UDCA005 English Translation Version

The minimum number of subjects required to have a power level of 80% at the 5% significance level is calculated as 138 per group. Taking into account the 20% withdrawal rate, this clinical study plans to enroll 173 people per group (total of 519).

Protocol No.: DW_UDCA005 English Translation Version

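### The SAP summarises time to gallstone by a median that cannot be reached at the planned rates; Kaplan-Meier cumulative incidence should replace it, and the prose should name the hazard ratio that the Cox code already requests

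*Protocol*

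**What the plan says.** Protocol section 14.4.2 says only that the time to gallstone formation will be shown by treatment group and compared by a Cox model. The SAP adds the detail. Section 8.4.2 reads: "For the time to gallstone formation, the median and corresponding 95% confidence intervals, and standard error values are presented". On the comparison of each dose with placebo, the same paragraph says that it "is analyzed using the Cox Proportional Hazards regression Model and the two-sided p-values are presented".

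SAP 6.1.2 runs the clock from gastrectomy. Subjects who finish without a stone are censored at completion, and those who withdraw are censored at withdrawal. Treatment lasts 52 weeks.

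The expected event rates are in the sample size sections. Protocol 8.3 states that "the incidence of gallstones in placebo was estimated to be 18" per cent. SAP 4.6 repeats this and takes for the study drug "7%, which is the weighted average of the three Ursodiol treatment groups in study 1".

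SAP 15.3 gives the Cox code. Its MODEL statement carries the RL option, which requests confidence limits for the hazard ratio. Its CONTRAST statement carries ESTIMATE=EXP, which requests the contrast on the hazard ratio scale.

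**The concern.** A Kaplan-Meier median exists only if the curve falls to 50%. If the plan expects fewer than one subject in five to have the event before follow-up ends, the chosen summary will show as not estimable in each arm. The reader then learns nothing from it about how the risk of a stone builds up over the year.

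The loss is modest but real. The plan allows for 20% withdrawal, and SAP 12.1.1 analyses efficacy data as observed cases without replacement. Time to gallstone is the efficacy endpoint that explicitly censors withdrawn subjects. A Kaplan-Meier risk from it would be a natural companion to the crude proportions under dropout, and the median does not supply that risk.

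The prose on the Cox model is also thinner than its neighbours. For the logistic endpoints, 8.4.2 names odds ratios, 95% intervals and p-values. For Cox it names p-values only, so the text does not match what the code in 15.3 asks for.

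**Working it through.** **Inputs.** The rates are 18% (placebo) and 7% (each DWJ1319 dose) at 12 months, from Protocol 8.3 and SAP 4.6. There are 138 per group before dropout and 173 enrolled. Follow-up is 52 weeks of treatment, with randomisation within 2 weeks of gastrectomy. Censoring follows SAP 6.1.2.

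**The plan's own figures reproduce.**
- Weighted averages: (18+112+6)/(56+661+44) = 136/761 = 17.9%, and (7+1+4)/(53+61+63) = 12/177 = 6.8%.
- Sample size: (1.96+0.842)² × {0.07×0.93 + 0.18×0.82} / 0.11² = 7.851 × 0.2127 / 0.0121 = 138.0.
- Dropout: 138/0.8 = 172.5, hence 173.

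**Is the median reached?** The stone-free proportion at 12 months is 1 − 0.18 = 0.82 on placebo and 1 − 0.07 = 0.93 on DWJ1319. Expected events with 138 per arm are 138×0.18 = 24.8 and 138×0.07 = 9.7. Half the arm is 69. The binomial chance of 69 or more events is about 1×10⁻¹⁷ at 18% and 3×10⁻⁴² at 7%.

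**Is either confidence limit of the median reached?** The lower limit is the first time at which the lower confidence bound of the curve falls to 0.50. With 138 followed to 12 months:
- Placebo: SE = √(0.82×0.18/138) = 0.0327, so the 95% interval is 0.756 to 0.884. The distance from 0.50 is z = 0.32/0.0327 = 9.8 (6.2 in absolute value on the log-log scale).
- DWJ1319: SE = √(0.93×0.07/138) = 0.0217, so the interval is 0.887 to 0.973 and z = 19.8 (7.0 on the log-log scale).

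Neither limit is reached in any arm.

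**How far off is the median?** Under an assumed constant hazard it is 12 × ln(0.5)/ln(0.82) = 42 months on placebo and 12 × ln(0.5)/ln(0.93) = 115 months on DWJ1319. Visit windows of one or two weeks do not change this.

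**Stress check.** Suppose the 12-month placebo rate were Study 1's 18/56 = 32.14%. Then 68% are stone-free, the interval is about 0.60 to 0.76, and the chance of 69 events in 138 is about 1×10⁻⁵. That 32.14% is a 6-month figure in obese patients. Carried on at a constant hazard for a further 6 months it would give (38/56)² = 0.46, and the placebo median would come within reach. The plan does not assume this, and its two gastric cancer sources give 16.94% and 13.64% at 12 months. Study 1's 300 mg arm carried on in the same way would still be at (46/53)² = 0.75.

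**What the endpoint can deliver.** Under proportional hazards the planned rates imply HR = ln(0.93)/ln(0.82) = 0.37. With 138 per group there are 24.8 + 9.7 = 34.5 events per comparison and SE(log HR) = √(1/24.84 + 1/9.66) = 0.379. The approximate 95% interval is 0.17 to 0.77. Schoenfeld power is Φ(√(34.5/4) × |ln 0.366| − 1.96) = Φ(0.99), about 84%. With 173 per group and no dropout there are about 43 events, the interval is 0.19 to 0.71, and power is about 91%.

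**The case against.** The strongest reply is that little is lost. An unreached median is reported as such and misleads nobody, and the trial's conclusion rests on the primary logistic test. Crude proportions within 3, 6, 9 and 12 months are already planned, with 95% intervals per arm (Protocol 14.4.2) and odds ratios with intervals (SAP 8.4.2). Kaplan-Meier figures at the same times would look much like them.

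Most of that stands, and it is why the point is minor. What remains is that the observed-case proportions do not adjust for censoring, and under 20% planned withdrawal a Kaplan-Meier estimate does. The refinement has limits. Stones are found at three-monthly imaging, so event times follow the visits, and the estimate assumes that withdrawal is unrelated to stone risk.

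A reader might infer from the p-value wording that this endpoint yields no usable effect estimate, or that every cell of its table will be empty. The documents do not support that. RL and ESTIMATE=EXP in SAP 15.3 request hazard ratios with limits, and the Cox p-values are estimable. The standard error in 8.4.2 is not tied to a named statistic, so it may not be lost with the median. The mock-up tables are not reproduced in the text, so the table cannot be shown to omit the hazard ratio. The gap is between prose and code.

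**Conclusion.** The point holds in a limited form. At the plan's own rates, neither the median time to gallstone nor its confidence limits will be estimable in any arm, so the descriptive summary in SAP 8.4.2 is uninformative. This rests on 12-month rates near 18% and 7% and follow-up that ends at about 12 months. It still holds with a 32% placebo rate at 12 months. A curve might drop below 50% at the very end through a handful of subjects still at risk in the last visit window, but a median obtained that way would mean nothing.

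On the Cox comparison the finding is one of alignment. Section 8.4.2 does not commit in words to the hazard ratio and interval that the code in 15.3 requests. The primary endpoint, the fixed-sequence test and the sample size are untouched.

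**What to change.** In SAP 8.4.2:

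1. Replace the median with Kaplan-Meier cumulative incidence and 95% confidence interval at 3, 6, 9 and 12 months for each arm. Say that these time points mean the scheduled visits. The clock starts at gastrectomy, while Visit 6 falls 12 months after randomisation, so an estimate read at exactly 12 months from surgery would miss stones found at Visit 6.
2. State that the Cox hazard ratio with 95% confidence interval is reported for each dose against placebo, beside the p-value.

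While aligning the text with 15.3, check the CONTRAST line. If treatment enters with three levels under reference coding and placebo is the last level, the coefficients 1 and −1 compare the two active doses, although the label says versus placebo. The RL hazard ratios would still be the wanted comparisons.

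The cost is a few sentences in the SAP and one table shell. No data collection, visit or sample size changes.
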